9.2.3. Peak NAC TNSS (0-1hr)

Peak TNSS (0-1hr) during the NAC will be analyzed using a longitudinal repeated measures model on data from years 1, 2, and 3 with a covariate for baseline Peak TNSS (0-1hr). All model details per the primary endpoint analysis apply.

For each year’s visit, the peak TNSS will be calculated as the maximum TNSS across all time points during the NAC from 0 to 1 hour.

If any of the “post” timepoints where the peak is expected to occur for each participant (i.e. 5 minutes, 15 minutes, or 30 minutes post) are missing, then the peak TNSS will be set to missing for the main analysis. Sensitivity analyses will be done to include these participants where their missing timepoints will be filled in, as part of a similar multiple imputation (MI) analysis as described in [Section 9.1.3](#) above (assuming MAR).

9.2.4. Size of early and late intradermal skin test response

The size of the early intradermal test response for *Phleum pratense* will be analyzed using a longitudinal repeated measures model on data from years 1, 2, and 3. A similar model will be used to analyze the late intradermal test response.

For analysis purposes, only the average of left and right arm sizes for *Phleum pratense* will be included in the model for each participant and visit (including baseline). In the rare case if only left (or only right) arm size is present, then the analysis value will be set to the single non-missing size. The sizes measured using Saline will not be analyzed.

For approximately 15 participants at the baseline visit, only a 1 BU dose of *Phleum pratense* test concentration was used instead of 10 BU. At the remaining visits for years 1, 2, and 3, the 10 BU concentration was used for all participants. The model-based analyses will be carried out in two ways:

- 1.) Main model for key secondary endpoint and multiplicity control: Using all participant results where both 1 BU and 10 BU test concentrations are considered. The following additional covariates will be included in the model, to adjust for the differing baseline values among participants:
 - a) size of the test response at baseline
 - b) categorical fixed effect for test concentration (1 BU versus 10 BU) at baseline
 - c) two-way interaction effect between a) and b)

- 2.) Exploratory model: Including only participants where the intended 10 BU test concentration was used across all visits, i.e. excluding the participants who had a 1 BU test concentration at baseline. A covariate for the size of the test response at baseline will be included.

9.2.5. Size of skin prick test endpoint titration response

The wheal size of the skin prick test endpoint titration response will be assessed for increasing concentrations of *Phleum pratense*, at each year during the study. The following concentrations will be assessed: 10 SQ-U/mL, 100 SQ-U/mL, 1000 SQ-U/mL, 10000 SQ-U/mL, and 100000 SQ-U/mL.

For analysis purposes, the wheal size used for analyses will be calculated as follows:

- The average of left and right arm wheal sizes will be calculated at each year (including the baseline year) for each participant and concentration.
- After taking the average of the left and right arm wheal sizes, the negative control will be subtracted out.
- In the rare case if only left (or only right) arm wheal size is present, then the analysis value will be set to the single non-missing size, minus negative control.
- If the subtraction of the negative control causes the final average wheal size to be <0mm, then a value of 0mm will be imputed for analysis purposes

In addition to the average wheal size, the Provocative Concentration at 5mm (also known as PC5) will be calculated as follows:

- An individual's average wheal size will be plotted per year, for each increasing concentration in a dose-response fashion, on a base-10 log scale where 10 SQ-U/mL = 1, 100 SQ-U/mL = 2, 1000 SQ-U/mL = 3, and so on.
- Using linear interpolation, the PC5 will be derived as the *minimum* concentration (on the base-10 log scale) for which an average wheal size of 5mm was met. This is calculated by taking a weighted average of the concentrations for the two points on either side of 5mm, for the *first* time (i.e. minimum concentration) the average wheal size exceeds 5mm for a given participant. In this case, the PC5 will be fractional value; for example, a PC5 = 2.65 refers to a concentration (on the base-10 log scale) partway between 100 SQ-U/mL (i.e. 2 on log scale) and 1000 SQ-U/mL (i.e. 3 on log scale).
- In the case in which a participant's average wheal size is exactly 5mm and this is the earliest (i.e. *minimum* concentration) at which 5mm is crossed, then the PC5 will be derived as this integer concentration (on the base-10 log scale).
 - In the special case that a participant's average wheal size exceeds 5mm and then drops to exactly 5mm at a higher concentration, the PC5 will be still be derived using the linear interpolated calculated value from the *first* time 5mm is exceeded (as opposed to the later/higher concentration when 5mm was exactly met).

- In the case in which a participant's average wheal size does not exceed 5mm at any of the five concentrations, an arbitrary value of 1000000 SQ-U/mL (i.e. a factor 6 on the base-10 log scale) will be imputed for that participant/year.

The skin prick test endpoint titration response will be analyzed using two different modelling approaches:

1. Main model for key secondary endpoint and multiplicity control: The PC5 (on the base-10 log scale) will be analyzed using a longitudinal repeated measures model on data from years 1, 2, and 3 with a covariate for the PC5 at baseline (i.e. Visit 0).
2. Supportive model: A multivariate repeated measures model will be constructed using a direct Kronecker product covariance structure for the distinct repeated effects of year (3 levels) and concentration (5 levels); see Galecki 1994. This model allows each participant to have each of their concentrations and each of their years of post-baseline data considered in the same model. An unstructured covariance matrix product with a second unstructured covariance matrix (SAS option UN@UN) will be assumed to model the correlation among year and concentration within a participant. If there are convergence issues with this matrix type, then the best fitting and most parsimonious alternative matrix will be used. The LS means with associated 95% CIs will be plotted for each treatment arm by year and concentration to examine which concentrations of grass pollen allergen caused a clinically meaningful skin wheal size at different thresholds (including at 3mm and 5mm). The treatment effect will be estimated from the LS means treatment differences in wheal size for each combination of year and concentration.

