13.3.4.1 Clinical Tolerance Endpoints

Peak nasal inspiratory flow, defined as the change in PNIF relative to the pre-allergen exposure PNIF measurement during the NAC (Delta PNIF AUC_{0-1hr}), will be analyzed using a longitudinal repeated measures model on data from years 1, 2, and 3 with a covariate for baseline Delta PNIF AUC_{0-1hr}.

The size of the early intradermal test response will be analyzed using a longitudinal repeated measures model on data from years 1, 2, and 3 with a covariate for the size of the early intradermal test response at baseline. A similar model will be used to analyze the late intradermal test response.

The size of the skin prick test endpoint titration response will be analyzed using a longitudinal repeated measures model on data from years 1, 2, and 3 with a covariate for the size of the skin prick test endpoint titration response at Visit 0.

Weekly seasonal symptoms (VAS 0-10 cm), CSMS and miniRQLQ will be summarized separately using the trapezoidal rule to estimate the VAS AUC, CSMS AUC, and miniRQLQ AUC at baseline, year 1, 2, and 3 respectively. The AUC of pollen counts collected weekly during the pollen season in year 1, 2, and 3 will be estimated similarly. A longitudinal repeated measures model will be applied to VAS AUC, CSMS AUC, and miniRQLQ AUC from years 1, 2, and 3 with a time-varying covariate for the AUC of pollen count and a covariate for baseline VAS AUC, baseline CSMS AUC, or baseline miniRQLQ AUC respectively.

MRSUI will be analyzed using a longitudinal repeated measures model on data measured twice (in-season in June/July and out-of-season in November/December) in years 1, 2, and 3 with a time-varying covariate for baseline in-season and out-of-season MRSUI.

Global Evaluation No. 1 will be analyzed using a longitudinal repeated measures model on data from years 1, 2, and 3 with a covariate for baseline Global Evaluation No. 1.

Global Evaluation No. 2 will be analyzed using a longitudinal repeated measures model on data from years 1, 2, and 3 without any additional covariates.

Using each of the above models, Secondary Objective 1 will be addressed by applying a contrast in least squares means at year 3 between the combination of SLIT and dupilumab arm and double-placebo arm.

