9.2. Secondary Endpoints

All secondary endpoints denoted as “key” per the multiplicity control testing algorithm (see [Section 8.5](#)) are alpha-controlled. The remaining secondary endpoints, including time points and pairwise comparisons that do not appear explicitly in Table 2: Endpoints with Multiplicity Control of this SAP, will be treated as supportive and are not alpha-controlled; therefore p-values are to be treated as descriptive only.

Unless otherwise noted, all secondary endpoint analyses will be performed on data from the mITT sample using a similar model methodology as per the primary endpoint analysis as described in [Section 9.1.2](#) above. All the same model stipulations apply including the inclusion of fixed effects for treatment arm (all 3 levels), time (i.e. year), and treatment arm by time interaction. Any additional baseline covariates that apply for a given secondary endpoint are noted in each sub-section below.

All pairwise treatment differences will be presented for each year post-treatment, as estimated by the models. Unless otherwise specified, the secondary endpoints will focus on the comparison for:

- Combination of SLIT and dupilumab arm *versus* double-placebo arm

The exploratory endpoints will focus on the remaining pairwise treatment comparisons (see [Section 9.3](#)).

Clinical tolerance endpoints will come from the model estimates at year 3, one year after completion of study treatment; whereas clinical desensitization endpoints will come from the model estimates at year 1 and 2 whilst on study treatment.

If a large departure from normality is found from model assumption testing, then log-transforming the outcome variable of interest prior to modeling or switching to a non-parametric test at each time point, may be performed instead.

9.2.1. TNSS AUC_{0-1hr} at years 1 and 2

The same model as for the primary analysis of TNSS AUC_{0-1hr} above will be used to estimate the LS means treatment difference at years 1 and 2 for the pairwise treatment difference between the combination of SLIT and dupilumab arm *versus* double-placebo arm.

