The score for each outcome at years 1, 2, and 3 will be analyzed using a multivariate repeated measures model constructed using a direct Kronecker product covariance structure for the distinct repeated effects of year (3 levels) and week (10 levels); see [Section 9.2.5](#) above for more model details. For the baseline season, a mean score for each outcome will be calculated across the “in-season” weeks such that there is a single baseline mean score for each participant; this baseline mean score will be included in the model as an additional covariate. An unstructured covariance matrix product with a second unstructured covariance matrix (SAS option UN@UN) will be assumed to model the correlation among year and week within a participant. If there are convergence issues with this matrix type, then the best fitting and most parsimonious alternative matrix will be used (for example, SAS option UN@AR(1) which models the effect of week using a first-order autoregressive structure). The LS means with associated 95% CIs will be reported for each treatment arm, year, and week.

To estimate a “yearly average” treatment effect for the main analysis, the LS means for each treatment will be calculated from the model estimates using the average of only the “in-season” weeks, for each year. The LS means treatment difference with associated two-sided p-value will be reported for each pairwise difference, for each year (again using only the “in-season” week estimates).

There will be 100 samples imputed for each MI analysis, and results will be summarized across the 100 MI samples. Only participants with a baseline visit (for the score being modelled) will be included in the main analyses. Sensitivity analyses may be considered to include participants where their entirely missing baseline visit will be filled in as part of the MI imputations.

Note as per [Section 8.5](#), only the mean CSMS model results at year 3 (using “in-season” data) will be part of the multiplicity control. Therefore, the supportive model for CSMS (using all data collected) and the models for the component scores of VAS and medication score will be considered supportive and may still have p-values reported for descriptive purposes only.

For the supportive analyses using all data collected, the LS means for each treatment (and their differences) will be calculated from the *same* main analysis model, using the model estimates from all 10 weeks per year.

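### The supportive skin prick model in SAP 9.2.5, the only one with wheal size as outcome, names no baseline covariate although Visit 0 wheal size is available at each concentration

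*SAP*

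**What the plan says.** **Protocol 13.3.4.1** plans one repeated measures model for the size of the titration response at years 1, 2 and 3, "with a covariate for the size of the skin prick test endpoint titration response at Visit 0".

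**SAP 9.2.5** replaces this with two models.

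- The main, alpha-controlled model takes PC5 as outcome, "with a covariate for the PC5 at baseline (i.e. Visit 0").
- The supportive model takes wheal size as outcome: "A multivariate repeated measures model will be constructed using a direct Kronecker product covariance structure for the distinct repeated effects of year (3 levels"), with concentration (five levels) as the other repeated effect. Each participant has "each of their years of post-baseline data considered in the same model". Its output is defined as follows: "The treatment effect will be estimated from the LS means treatment differences in wheal size for each combination of year and concentration". No baseline term is mentioned.

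**SAP 9.2** governs all secondary models. It says they follow the primary methodology and lists arm, year and their interaction as carried over. It then adds: "Any additional baseline covariates that apply for a given secondary endpoint are noted in each sub-section below".

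**Baseline data.** Protocol Appendix 2 schedules the titration at Visit 0, 1 to 3 hours before the first dupilumab or placebo injection. SAP 9.2.5 lists the five concentrations and derives the analysis value at baseline too: "The average of left and right arm wheal sizes will be calculated at each year (including the baseline year) for each participant and concentration".

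**The concern.** Visit 0 skin reactivity is measured and derived at each concentration, and the protocol adjusts the size of the response for it. The model that analyses size does not mention it. Baseline cannot enter as a response level either, since only post-baseline years are used.

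If the model is fitted as written, stable differences in skin reactivity between participants stay in the error term. Any chance imbalance between arms at Visit 0 also passes into the follow-up differences, in proportion to the baseline-to-follow-up correlation. At stake is the precision of 3 years × 5 concentrations = 15 wheal-size differences for each arm comparison. These are the plan's only estimates of how far wheal size itself changed: PC5 keeps only the first crossing of 5 mm, and assigns a fixed value of 6 on the log scale to participants who never reach it.

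**Working it through.** **1. Is the covariate absent? The related models side by side.**

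| SAP model | Baseline term |
|---|---|
| 9.2.4 intradermal, main and exploratory | stated in both |
| 9.2.5 PC5 | stated (Visit 0 PC5) |
| 9.2.5 wheal size, year by concentration | not mentioned |
| 9.2.6 seasonal scores, year by week, same Kronecker form | stated: "this baseline mean score will be included in the model as an additional covariate" |
| 9.2.7 miniRQLQ, same form | stated |
| 9.2.9 Global Evaluation No. 2 | stated that there is none |
| 9.3.2 sneeze count | stated that there is none, with the reason |

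Section 9.2.6 refers back to 9.2.5 for model details and then adds its baseline mean as something additional. In this comparison, only the wheal-size model is silent.

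**2. The plan's own precision figure.** The documents give no power or precision figure for wheal size. The only one is in Protocol 13.6, for TNSS AUC: 30 per arm, two-sided alpha 0.05, 80% power, placebo mean 3.81, SD 1.53 to 1.73, detectable reduction 29% to 33%.

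Detectable reduction = (1.960 + 0.842) × SD × √(2/30) / 3.81

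- SD 1.53: 1.107 / 3.81 = 29.0%
- SD 1.64: 1.186 / 3.81 = 31.1%
- SD 1.73: 1.251 / 3.81 = 32.8%

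This reproduces the stated range. The same 30 per arm is used below.

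**3. Precision with and without adjustment.** Let rho be the correlation between Visit 0 and follow-up wheal size at the same concentration. The documents do not give it, so a range is shown.

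- Unadjusted standard error (SE) of an arm difference = √(2/30) = 0.258 SD.
- Proportional fall in variance with adjustment ≈ rho².
- Adjusted SE = 0.258 × √(1 − rho²) × √(1 + 1/85). The last factor is the cost of estimating the slope, with 90 participants in three arms (90 − 5 = 85).

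| rho | Fall in variance (rho²) | Adjusted SE (SD units) | SE ratio | Excess width of unadjusted interval | Equivalent sample size |
|---|---|---|---|---|---|
| 0.1 | 1% | 0.258 | 1.00 | none | 1.00 times |
| 0.3 | 9% | 0.248 | 0.96 | 4% | 1.09 times |
| 0.5 | 25% | 0.225 | 0.87 | 15% | 1.32 times |
| 0.7 | 49% | 0.185 | 0.72 | 39% | 1.94 times |

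A simulation with three arms of 30 and Kronecker-structured data compared the year 3 difference at the top concentration with and without the baseline covariate. It gave SE ratios of 0.95, 0.87 and 0.74 at rho 0.3, 0.5 and 0.7. It used least squares on that one cell, not the full model.

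**4. The same in power terms.** The starting powers are also assumptions. By two-sample t test with 30 per arm, a standardized difference of 0.736 has 80.0% power. Dividing by √(1 − rho²) gives 0.772, 0.850 and 1.031, with power 83.6%, 89.9% and 97.5%. Starting from 60%, power becomes 64.1%, 72.4% and 87.3%. A normal approximation that includes the slope-estimation factor takes 80% to 83.1%, 89.5% and 97.4%.

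**5. Chance imbalance.** With 30 per arm, a one-SE imbalance at Visit 0 is 0.258 SD. It moves the unadjusted follow-up difference by about rho × 0.258 = 0.077, 0.129 or 0.181 SD at rho 0.3, 0.5 or 0.7.

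**The case against.** **The omission is by silence.** The supportive paragraph lists no fixed effects at all, not even treatment arm. These must come from SAP 9.2, which says the primary model's provisions hold, and the primary model has a baseline covariate. The sentence on covariates also speaks of sub-sections, not of each model, and 9.2.5 does note one, for PC5. The explicit statement in 9.2.6 may be there only because its baseline is a newly derived mean. This stands as far as making the text ambiguous. It does not reverse the reading: SAP 9.2 names what carries over (arm, year, interaction) and treats baseline covariates separately. In 9.2.4, where one sub-section also holds two models, each states its own.

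**A reader might infer that the SAP drops a covariate the protocol required for this model.** The documents do not support that. Protocol 13.3.4.1 describes a single model of size and does not say which concentration or summary defines size. The year-by-concentration model is a SAP addition. SAP Table 2 defines the titration endpoint through PC5, and the Visit 0 covariate carries over to that model. The protocol shows that baseline adjustment was thought appropriate for this response, but it does not prescribe it for the supportive model. So leaving the covariate out of the changes listed in SAP section 13 is not in itself an error.

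**A reader might also infer biased differences or a weakened key secondary test.** Neither follows. Randomization keeps the unadjusted differences unbiased, and the PC5 test is separately modelled and already adjusted.

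**Little depends on it, and the size is assumed.** The model is supportive, outside multiplicity control, with descriptive p-values. Both points stand. Wheals are also floored at 0 mm after control subtraction, so rho may be low at the weakest concentrations, and one rho need not fit all 15 cells. This limits the importance of the point, but a pre-treatment covariate already in hand is still worth using.

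**Conclusion.** The concern holds as a correctable weakness in a supportive analysis. As written, SAP 9.2.5 most naturally gives a wheal-size model without baseline adjustment, although the covariate is measured before treatment and already derived. The differences stay unbiased but are less precise, and more exposed to chance imbalance at Visit 0, than they need to be.

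The avoidable share of the variance is about 9%, 25% or 49% at rho 0.3, 0.5 or 0.7. There is no gain near 0.1, and possibly little at the lowest concentrations. These figures rest on an assumed rho, on 30 per arm, and on reading SAP 9.2 as not supplying the covariate. If the other reading was intended, the text still allows two analysts to fit different models, and the same sentence settles it.

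**What to change.** Add to the supportive model in SAP 9.2.5: *The Visit 0 average wheal size (negative control subtracted) at the same concentration is included as a covariate, with a slope that may differ by concentration.*

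The note at the end of the SAP shows that the plan is final and the database locked. The sentence should therefore be a dated clarification, stating that the covariate follows the baseline adjustment in Protocol 13.3.4.1 and was not chosen from results. If the unadjusted model has already been run, report it beside the adjusted one.

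No new data are needed. The cost is five slopes (one per concentration) in a model for which the SAP already anticipates convergence trouble, and the loss of any participant without a Visit 0 titration, who would also lack the baseline covariate in the PC5 model. If the sponsor prefers no adjustment, 9.2.5 should say so and give the reason, as the SAP does for the sneeze count.

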9.2.6. Seasonal outcome 1: Weekly seasonal symptoms VAS 0-10, Medication scores, and CSMS

Weekly seasonal symptoms (Visual Analogue Scale [VAS] 0-10 cm), medication scores, and combined symptom medication score (CSMS) were collected over the course of 10 weeks from approximately the end of May through end of July, for each year of the study:

- 2021 (baseline season)
- 2022 (year 1)
- 2023 (year 2)
- 2024 (year 3)

Within a given year, the definition of a pollen season will be programmatically derived using Protocol Table 6 as shown below:

	Pollen Season	Peak pollen season	High pollen days
Start of season	1st day of 5 days (out of 7 consecutive days) each of these 5 days with ≥ 3 pollen/m ³ and with a sum of these 5 days of ≥ 30 pollen/m ³	1st day of 3 consecutive days, each with at least ≥ 50 pollen/m ³	The day(s) with at least 50 pollen/m ³
End of season	Last day of series of 5 days (out of 7 consecutive days) with ≥ 3 pollen/m ³ and with a sum of these 5 days of ≥ 30 pollen/m ³	Last day of at least 3 consecutive days, each with ≥ 50 pollen/m ³	

The following two timeframes will be used for analysis:

- only the values collected during weeks which are determined to be “in-season” according to the above table’s definition of “Pollen Season”
- all data collected i.e. up to 10 values per participant per year

The main model for analyses (including for the key secondary endpoint of CSMS) will estimate treatment effects from only the “in-season” weeks, whereas supportive analysis models will use all data collected.

The following three outcomes will be analyzed separately:

- VAS score
- Medication score
- CSMS (combination of VAS and medication score)

The score for each outcome will be analyzed for each of the 10 weeks at each year (including the baseline year). A multiple imputation (MI) approach, similar to the approach described in [Section 9.1.3](#) above, will be used to fill in missing values prior to modelling the score of each outcome at each week per year. Missing at random (MAR) will be assumed given the sporadic missingness of the values at each week.

The score for each outcome at years 1, 2, and 3 will be analyzed using a multivariate repeated measures model constructed using a direct Kronecker product covariance structure for the distinct repeated effects of year (3 levels) and week (10 levels); see [Section 9.2.5](#) above for more model details. For the baseline season, a mean score for each outcome will be calculated across the “in-season” weeks such that there is a single baseline mean score for each participant; this baseline mean score will be included in the model as an additional covariate. An unstructured covariance matrix product with a second unstructured covariance matrix (SAS option UN@UN) will be assumed to model the correlation among year and week within a participant. If there are convergence issues with this matrix type, then the best fitting and most parsimonious alternative matrix will be used (for example, SAS option UN@AR(1) which models the effect of week using a first-order autoregressive structure). The LS means with associated 95% CIs will be reported for each treatment arm, year, and week.

To estimate a “yearly average” treatment effect for the main analysis, the LS means for each treatment will be calculated from the model estimates using the average of only the “in-season” weeks, for each year. The LS means treatment difference with associated two-sided p-value will be reported for each pairwise difference, for each year (again using only the “in-season” week estimates).

There will be 100 samples imputed for each MI analysis, and results will be summarized across the 100 MI samples. Only participants with a baseline visit (for the score being modelled) will be included in the main analyses. Sensitivity analyses may be considered to include participants where their entirely missing baseline visit will be filled in as part of the MI imputations.

Note as per [Section 8.5](#), only the mean CSMS model results at year 3 (using “in-season” data) will be part of the multiplicity control. Therefore, the supportive model for CSMS (using all data collected) and the models for the component scores of VAS and medication score will be considered supportive and may still have p-values reported for descriptive purposes only.

For the supportive analyses using all data collected, the LS means for each treatment (and their differences) will be calculated from the *same* main analysis model, using the model estimates from all 10 weeks per year.

It may be explored if adding a time-varying covariate for the weekly mean of grass pollen counts to the model significantly improves model fit, and if so, will be included as an extra covariate in the main analysis model.

